#### 5.2.14 Unscheduled Visits

Only scheduled post-baseline values will be tabulated. Post-baseline repeat / unscheduled assessments will in general be disregarded, although unscheduled visits will be included in the derivation of shifts to "worst" post-baseline value. All post-baseline assessments (scheduled and unscheduled) will be listed in the relevant appendices to the CSR.

#### 5.2.15 Randomization Strata

Randomization of participants to treatment arm is stratified by fludrocortisone treatment and where applicable, the analyses will be stratified by baseline biochemical control status.

# 5.3 General Considerations

#### 5.3.1 Tables and Listings

All data listings, summaries, figures and statistical analyses will be generated using SAS [SAS Institute Inc., Cary, NC, 27513, USA] version 9.4 or higher.

Summaries will be presented by treatment group (Chronocort vs IRHC).

Overall columns are to be included within the table shells as follows:

Disposition	Treatment group and overall
Demography and Baseline	Treatment group and overall
Characteristics	
Prior, Concomitant, Subsequent	Treatment group and overall
and Rescue Medications	
Exposure to Study Drug	Treatment group only

Efficacy	Treatment group only
AEs	Treatment group and overall
Other safety	Treatment group only

Listings will be sorted in the following order: treatment group, participant, parameter, and visit unless otherwise stated. All data will be listed; participants who were not randomized will be displayed after the randomized treatment groups as "Not randomized to study treatment".

Continuous variables will be summarized by the number of non-missing observations, mean, median, standard deviation, quantiles and minimum and maximum. For tabulations of changes from baseline data for efficacy endpoints, the lower and upper 95% confidence limits for the mean for the individual treatments will be presented.

Categorical variables will be summarized by presenting the frequency and percent. Percentages will be based on the number of non-missing observations or the participant population unless otherwise specified. For each variable, all categories will be shown. Zero frequencies (but not the percent) within a category will be presented.

#### 5.3.2 Decimal Places

Decimal places for derived data described in Section 5.2 will be determined by the scale of measurement unless otherwise stated. No decimal places will be displayed if the smallest calculated value is  $\geq$  100; 1 decimal place will be displayed when the smallest value is within the interval (10, 100), with 10 being inclusive; 2 decimal places will be displayed when the smallest value is within (1, 10), with 1 being inclusive; and so on for even smaller scales of measurement.

Derived data where it is known in advance the result will be an integer, for example day, month, year, number of days and total scores (for rating scales) will be presented with zero decimal places.

Means, medians and percentiles will be displayed to one more decimal place than the data, dispersion statistics (e.g. standard deviation) will have two more decimal places, and the minimum and maximum will be displayed to the same number of decimal places as reported in the raw data. Percentages will be displayed with one decimal place.

P-values will be quoted to 3 decimal places. P-values < 0.001 will be presented as "p<0.001". Where this value is less than 0.05 (two-sided test), 0.025 (one-sided test), 0.01 or 0.001, attention will be drawn to this fact using the conventional "\*", "\*\*" or "\*\*\*" annotation, respectively. These conventions will be footnoted in the table or figure shell.

#### 5.4 Participant Disposition

Participant disposition will be summarized descriptively as follows:

- The number and percentage of participants achieving the following criteria will be summarized by treatment group and overall for the Screened Set:
  - Entering the study or failed screening, with reasons
  - Multiple screened and a) entering the study or b) persistent failed screening
  - Received IRHC in the run-in period but were not randomized, with reasons
  - Randomized
  - Included and excluded from each analysis set, with reasons for exclusion
  - Completed or prematurely discontinued treatment, with reasons (including the number of participants with premature discontinuation of study treatment, that continued study assessments)
  - Completed or prematurely discontinued study, with reasons
- As a separate summary, the number of participants included in each analysis set will be summarized for each region, country and study site by treatment group and overall for the Screened Set.
- The number of participants who complete each phase of the study and the number of participants present at each scheduled visit will be summarized by treatment group and overall for the FAS.

Participant disposition will be listed for the Screened Set. The reasons for exclusion from each of the analysis sets will also be listed.

#### 5.5 **Protocol Deviations**

A critical protocol deviation is a protocol deviation (PD) with the potential to compromise the efficacy analysis. Critical PDs may include, but are not limited to:

- Randomization criteria violations.
- Inclusion/exclusion criteria violations.
- Inadequate compliance with study drug.
- Prohibited medications taken.
- Significant deviations from the study drug administration schedule.
- Other protocol deviations that could affect participants' efficacy outcomes.

A Data Review Meeting will be convened after the data has been cleaned and the database softlocked but before final database lock and analysis has commenced. As part of the review, a determination will be made on whether PDs are classed as 'critical', 'major', 'minor' or not a PD

at all. The review will also document the allocation of participants to analysis sets, among other items.

A listing of all PDs defined as major and/or critical will be presented. Participants experiencing at least one major and/or critical PD, and the reasons for deviation will be summarized by treatment group and overall.

# 5.6 Demographic and Other Baseline Characteristics

Demographic and other baseline variables will be summarized by treatment group, split by baseline biochemical control status, using the FAS. The comparability of treatment groups with respect to participant demographics and baseline characteristics will be assessed in a descriptive manner; no formal statistical testing will be performed.

Standard continuous or categorical variable summaries will be presented by randomized treatment group for the following variables. Participant listings will also be presented.

- Demographic data (e.g. age, sex, race, ethnicity, height (cm), weight (kg), BMI (kg/m^2), fludrocortisone replacement status [as stratified for randomization, and actual if different], baseline biochemical control)
- Disease history (e.g. duration since diagnosis, hospitalization and number of adrenal crises within the 12 months prior to randomization, previous CAH medication)
- Medical history by MedDRA System Organ Class (SOC) and Preferred Term (PT)

All variables collected only at baseline or prior to baseline will be summarized here. Variables that are collected pre and post-baseline (e.g. vital signs, labs, physical exam, ECGs and efficacy) will be presented at Screening and/or Baseline in the by-visit tables within their respective analysis section (i.e. under efficacy or safety).

# 5.7 Medical History

Separate tabulations of previous and ongoing conditions at screening will be presented by treatment group and overall for the FAS. Conditions will be presented according to Medical Dictionary for Regulatory Activities (MedDRA, version 20.0 or later) primary system organ class and preferred term. The dictionary version used will be displayed in the footnote of the presented data displays.

# 5.8 Other Baseline Characteristics

Pregnancy test performed at screening, baseline and at other scheduled visits for females of childbearing potential will be listed only.

#### 5.9 Covid-19 Visit Impact

At each visit, using the FAS, a summary will be provided of any impact on the visit due to Covid-19. The number of participants with an impact will be summarized, as well as what the impact was (missed visit, interrupted and/or out of window in person visit at site, remote visit, other).

#### 5.10 Exposure to Study Drug

Extent of exposure will be presented using total treatment duration (days) by treatment group for the SAF.

The number and percentage of participants experiencing a study drug dose change (either increase or decrease) during the study, plus reasons for change, will be summarized by treatment group for the SAF. Total glucocorticoid exposure during the study will also be summarized by treatment group for the SAF.

#### 5.11 Efficacy Analyses

Analyses will be stratified or adjusted, as appropriate, on the basis of (i) the participant's fludrocortisone replacement status (requires fludrocortisone/does not require fludrocortisone) and (ii) whether they are in biochemical control at baseline or not (based on the androgen results from the baseline visit [Visit 2]).

#### 5.11.1 Statistical Hypotheses

# 5.11.1.1 Primary Efficacy Endpoint: Biochemical Response after 28 Weeks of Randomized Study Treatment

A participant is a biochemical responder if:

- they are in biochemical control at 08:00 hours after 28 weeks of randomized treatment (Visit 6)
   where 'biochemical control' is defined as a 17-OHP concentration equal to or less than the upper limit of optimal control and a A4 concentration equal to or less than the upper limit of the reference range if either or both these conditions are not met the participant is not in biochemical control, AND
- ii) their total daily dose after 28 weeks of randomized treatment is not more than 25 mg (if the participant was in biochemical control at baseline) and not more than 30 mg (if the participant was not in biochemical control at baseline).

The primary null hypothesis is that the response rate in the Chronocort arm is worse than or equal to the response rate in the IRHC arm minus 15 percentage points. The primary alternate hypothesis is that the response rate in the Chronocort arm is better than the response rate in the IRHC arm minus 15 percentage points. Biochemical non-inferiority of Chronocort to IRHC will be declared if the 95% CI for the difference in response rates between the 2 treatment arms (Chronocort minus IRHC) is wholly above minus 15 percentage points.

# 5.11.1.2 First Key Secondary Efficacy Endpoint: Dose Response after 28 Weeks of Randomized Study Treatment

A participant is a dose responder if:

- i) their total daily dose after 28 weeks of randomized treatment is not more than 25 mg, AND
- they are in biochemical control at 08:00 hours after 28 weeks of randomized treatment (Visit 6)
   where 'biochemical control' is defined as a 17-OHP concentration equal to or less than the upper limit of optimal control and a A4 concentration equal to or less than the upper limit of the reference range if either or both these conditions are not met the participant is not in biochemical control.

The first key secondary null hypothesis is that the response rate in the Chronocort arm is worse than or equal to the response rate in the IRHC arm. The first key secondary alternate hypothesis is that the response rate in the Chronocort arm is better than the response rate in the IRHC arm.

Dose superiority of Chronocort to IRHC will be declared if the two-sided 95% CI for the difference in response rates between the 2 treatment arms (Chronocort minus IRHC) is wholly above zero, provided that biochemical non-inferiority of Chronocort to IRHC has been declared under the primary efficacy objective.

# 5.11.1.3 Second Key Secondary Efficacy Endpoint: Mean Total Daily Dose of Hydrocortisone after 28 Weeks of Randomized Study Treatment

The second key secondary null hypothesis is that the mean total daily dose of hydrocortisone after 28 weeks of randomized treatment in the Chronocort arm is higher than or equal to the mean total daily dose after 28 weeks of randomized treatment in the IRHC arm. The second key secondary alternate hypothesis is that the mean total daily dose after 28 weeks of randomized treatment in the Chronocort arm is lower than the mean total daily dose after 28 weeks of randomized treatment in the IRHC arm.

Superiority of Chronocort to IRHC (with respect to the total daily dose after 28 weeks of randomized treatment) will be declared if the two-sided 95% CI for the difference in means between the 2 treatment arms (Chronocort minus IRHC) is wholly below zero, provided that biochemical non-inferiority of Chronocort to IRHC has been declared under the primary efficacy objective, and dose superiority of Chronocort to IRHC has been declared under the first key secondary efficacy objective.

Analysis	Statistical Analysis Methods
Primary analysis	Non-inferiority: a 95% CI will be calculated for the difference (Chronocort minus IRHC) in biochemical responder rates. Biochemical non-inferiority will be declared if the 95% CI lies wholly above minus 15%. The primary analysis will be conducted using the FAS.
First key secondary analysis	Superiority analysis: a 95% CI will be calculated for the difference (Chronocort minus IRHC) in dose responder rates. Dose superiority will be declared if the 95% CI lies wholly above zero, provided that biochemical non-inferiority of Chronocort to IRHC has been declared under the primary efficacy objective. The first key secondary analysis will be conducted using the FAS.
Second key secondary analysis	Superiority analysis: a 95% CI will be calculated for the difference (Chronocort minus IRHC) in mean total daily dose after 28 weeks of randomized treatment. Superiority with respect to total daily dose after 28 weeks of randomized treatment will be declared if the 95% CI lies wholly below zero, provided that biochemical non-inferiority of Chronocort to IRHC has been declared under the primary efficacy objective and dose superiority of Chronocort to IRHC has been declared under the first key secondary objective. The second key secondary analysis will be conducted using the FAS.
Other analyses of the primary outcome variable and of the key secondary outcome variables (classed as secondary outcome analyses)	
 
Analyses of the primary outcome variable other than the primary analysis and analyses of the key secondary outcome variables other than the key secondary analyses, such as: 
 
analysis at other timepoints
 
assessment of the effect of baseline and disease characterizing variables, including stratification variables
 
analysis using the EES and subgroups.
 
 
 
are deemed to be supplementary analyses and will be performed using the same statistical methodology as will be used for the primary analysis and key secondary analyses. Calculated p-values will be indicative rather than substantive.
 

# 5.11.1.4 Overview of Analyses for Efficacy Endpoints

Other secondary outcome variables and exploratory outcome variablesAnalysis of any other secondary outcome variables and of exploratory outcome variables will be performed using the standard statistical methodology. Calculated p-values will be indicative rather than substantive.
--------------------------------------------------------------------------------------------------------------------------------------------------------------------------------------------------------------------------------------------------------------------------------------------------------

#### 5.11.2 Estimands

#### 5.11.2.1 Primary Efficacy Endpoint

Treatment Conditions of Interest	Chronocort vs IRHC		
Population	Participants Aged 16 Years and Over with Congenital Adrenal		
-	Hyperplasia		
Assessment	17-OHP and A4 plasma concentration obtained from the 08:00		
	hours bloo	d sample at Visit 6 (EOS) and daily dose of	
	hydrocorti	sone	
Outcome Variable	The proportion of participants in each treatment arm who are		
	biochemic	al responders at 08:00 hours at Visit 6 (EOS). See Section	
	5.11.1.1 for details on criteria for biochemical response		
Population-Level Summary	The differe	ence (Chronocort arm minus IRHC arm) in the proportion	
	of particip	ants who are biochemical responders at 08:00 hours at	
	Visit 6 (EC	DS)	
Analysis	The difference (Chronocort arm minus IRHC arm) in the proportion		
	of particip:	ants who are biochemical responders is estimated using	
	logistic reg	gression (Ge, 2011) with treatment, fludrocortisone use at	
	baseline, b	baseline, biochemical control at baseline, and the interaction of	
	fludrocortisone use and biochemical control at baseline as		
	explanatory variables.		
Intercurrent Events (ICEs)	(i)	Participants who withdraw from treatment before Visit	
		6 (EOS) or who do not meet the criteria for being a	
		biochemical responder are deemed not to be a	
		biochemical responder.	
	(ii)	Participants receiving rescue medication (under 'stress	
		dosing rules') will continue in the study with unchanged	
		procedures, except that Visit 6 (EOS) will be delayed if	
		necessary, to 5 days after the use of rescue medication	
Strategies to Handle ICEs	(i)	Discontinuation of study treatment before Visit 6	
		(EOS), for any reason	
		Composite strategy	
	(ii)	Receipt of rescue medication under 'stress-dosing rules'	
	()	Treatment policy strategy	

Where under the treatment policy strategy, available data occurring on or after the ICE will be analyzed as observed, and under the composite strategy, any observed biochemical response data

after the ICE will be considered as biochemical non-response. Additionally, any missing Visit 6 biochemical response data will be multiple imputed per Section 5.11.3.1.

**Interpretation:** Biochemical non-inferiority of Chronocort to IRHC will be declared if the 95% CI for the difference in proportions lies wholly above minus 15 percentage points. Confirmatory testing will occur on the primary estimand.

Choice of Non-Inferiority Margin: See Section 3 for details on the choice of the NI margin.

Treatment Conditions of Interest	Chronocort vs IRHC		
Population	Participants Aged 16 Years and Over with Congenital Adrenal		
	Hyperplas	ia	
Assessment	17-OHP and A4 plasma concentration obtained from the 08:00		
	hours bloc	od sample at Visit 6 (EOS) and daily dose of	
	hydrocorti	isone	
Outcome Variable	The proportion of participants in each treatment arm who are dose		
	responder	s at 08:00 hours at Visit 6 (EOS). See Section 5.11.1.2 for	
	details on	criteria for dose response.	
Population-Level Summary	The difference (Chronocort arm minus IRHC arm) in the proportion		
	of particip	ants who are dose responders at 08:00 hours at Visit 6	
	(EOS)		
Analysis	The difference (Chronocort arm minus IRHC arm) in the proportion		
	of particip	ants who are dose responders is estimated using logistic	
	regression	(Ge, 2011), with treatment, fludrocortisone use at	
	baseline, b	biochemical control at baseline, and the interaction of	
	fludrocortisone use and biochemical control at baseline as		
	explanator	ry variables.	
ICEs	(i)	Participants who withdraw from treatment before Visit	
		6 (EOS) or who do not meet the criteria for being a	
		dose responder are deemed not to be a dose responder.	
	(11)	Participants receiving rescue medication (under 'stress	
		dosing rules') will continue in the study with unchanged	
		procedures, except that Visit 7 will be delayed if	
		necessary, to 5 days after the use of rescue medication	
Strategies to Handle ICEs	(1)	Discontinuation of study treatment before Visit 6	
		(EOS), for any reason	
		Composite strategy	
	(ii)	Receipt of rescue medication under 'stress-dosing rules'	
		Treatment policy strategy	

5.11.2.2 First Key Secondary Efficacy Endpoint

Note: Handling strategies for ICEs will be the same as for the primary efficacy endpoint.

**Interpretation:** Dose superiority of Chronocort to IRHC will be declared if the 95% CI for the difference in proportions lies wholly above zero, provided that biochemical non-inferiority of Chronocort to IRHC has been declared.

Treatment Conditions of Interest	Chronocort vs IRHC		
Population	Participants Aged 16 Years and Over with Congenital Adrenal		
	Hyperplasia		
Assessment	Total daily dose of hydrocortisone at Visit 6 (EOS)		
Outcome Variable	The mean total daily dose in each treatment arm at Visit 6 (EOS).		
Population-Level Summary	The difference (Chronocort arm minus IRHC arm) in the mean total		
	daily dose of hydrocortisone at Visit 6 (EOS)		
Analysis	The mean difference (Chronocort arm minus IRHC arm) in total		
	daily dose after 28 weeks of randomized treatment is estimated		
	using a repeated measures model on timepoints 10, 16 and 28		
	weeks after randomization with treatment, timepoint, treatment by		
	timepoint interaction, fludrocortisone use at baseline, biochemical		
	control at baseline, and the interaction of fludrocortisone use and		
	biochemical control at baseline as explanatory variables.		
ICEs	(i) Participants who withdraw from treatment before Visit		
	6 (EOS) will have their total daily dose imputed.		
	(ii) Participants receiving rescue medication (under 'stress		
	dosing rules') will continue in the study with unchanged		
	procedures, except that Visit 6 (EOS) will be delayed if		
	necessary, to 5 days after the use of rescue medication		
Strategies to Handle ICEs	(i) Discontinuation of study treatment before Visit 6		
	(EOS), for any reason		
	Treatment policy strategy		
	(ii) Receipt of rescue medication under 'stress-dosing rules'		
	Treatment policy strategy		
	······································		

# 5.11.2.3 Second Key Secondary Efficacy Endpoint

Where under the treatment policy strategy, available data occurring on or after the ICE will be analyzed as observed. Data missing at 28 weeks (or any other visit) will be imputed as per Section 5.11.3.3.

**Interpretation:** Superiority of Chronocort to IRHC with respect to total daily dose after 28 weeks of randomized treatment will be declared if the 95% CI for the difference in means lies wholly below zero, provided that biochemical non-inferiority of Chronocort to IRHC has been declared under the primary efficacy objective and dose superiority of Chronocort to IRHC has been declared under the first key secondary efficacy objective.

# 5.11.3 Estimand Related Data Handling

#### 5.11.3.1 Primary Efficacy Endpoint – Biochemical Response at Visit 6 (EOS)

For the imputation of biochemical response where a composite variable strategy is employed, any biochemical response data occurring on or after the applicable ICE will be considered as biochemical non-response. This imputation will occur first, before any imputation of missing data occurs.

For the imputation of missing data, the binary response status will be multiple imputed. The number of imputations will be 50, representing the set of 50 plausible values obtained from a prediction model based primarily on observed data (i.e. applying a MAR approach in general). The fully conditional specification (FCS) method will be used for dealing with arbitrary non-monotone missing data patterns. The FCS is based on an iterative algorithm; at each iteration and for each variable of the prediction model, there is a prediction step and an imputation step. As imputations will be for binary components, the models used for prediction and imputation will be logistic regression models.

The full MI approach will comprise of 4 steps, as follows:

- Prediction Step: the current (iteration) values of the observed and imputed values are used to derive the predictive distribution of the missing values under MAR conditions
- Imputation Step: updated imputations are generated by draws from the predictive distribution defined by the updated logistic regression model
- Analysis Step: The analysis as described in Section 5.11.4.1 is conducted for each of the 50 imputations
- Combining Step: Rubin's rule (SAS PROC MIANALYZE) is used to combine the 50 point estimates and standard errors, in order to provide a single point estimate and confidence interval that can be compared to the respective Non-inferiority delta in the null hypotheses described in Section 5.11.1 to provide rejection or acceptance.

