Participants will return to the study site for titration visits at 4, 10 and 16 weeks after randomization, with androgen levels assessed at each of these visits at 08:00 hours (before the morning dose of study medication) and 13:00 hours (± 30 minutes). At each of these 3 visits dose reductions (in 5 mg steps at each visit) can be conducted if required, based on androgen results and adrenal insufficiency symptoms collected using the adrenal insufficiency checklist. The decision to change doses in both treatment groups will be made by an independent blinded physician and the appropriate investigational medicinal product (IMP) packs will be sent to the participant, either to collect from their local study site or sent directly to the participant's home. The treatment packs for each participant will always contain the same number of capsules as the previous supplies (with placebo capsules masking any changes) to maintain the blinding and to ensure the participant is not aware of any dose changes.

Once the titration visit at 16 weeks is complete and the dose adjusted, if necessary, the dose of study medication will then be fixed and should remain unchanged until the end of study (EOS) visit (up to 12 weeks of fixed dose treatment) if possible. The last dose of study medication will be taken in the morning of the last dosing day.

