The goal of therapy in CAH is to reduce excessive androgen secretion by replacing the deficient glucocorticoid hormones [Speiser et al, 2010]. This study will achieve this goal by close monitoring of adrenal androgens (17-OHP and A4) and modifying the glucocorticoid dose in the light of biochemical control and clinical signs and symptoms of the adequacy of glucocorticoid replacement.

A participant is a dose responder if their dose after 28 weeks of randomized treatment is less than the starting dose of 30 mg/day, provided they are in biochemical control at that time. All

dose responders are biochemical responders: additionally, participants who were out of biochemical control at baseline but are in biochemical control after 28 weeks of randomized treatment are also biochemical responders, provided their dose at that time is not higher than the starting dose of 30 mg/day.

The primary efficacy analysis will be to compare Chronocort to IRHC in terms of biochemical responder rate after 28 weeks of randomized treatment. The first key secondary efficacy analysis will be to compare Chronocort to IRHC in terms of dose responder rate after 28 weeks of randomized treatment. The second key secondary efficacy analysis will be to compare Chronocort to IRHC in terms of total daily dose after 28 weeks of randomized treatment.

In addition, clinical endpoints will be assessed over the course of the study to evaluate the impact on participants' QoL and other clinical consequences of CAH.

[REDACTED]

Subject reported outcomes were used in studies DIUR-003, DIUR-005 and DIUR-006, and these have also been included in this study.

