#### 5.11.3.1.1 Prediction Step

The prediction step attempts to predict the biochemical response based on observed data that may have an influence on it (assuming MAR).

The prediction model will include the following variables, to attempt to estimate the missing value as closely as possible based on available characteristics.

Timepoint	Variables
Variable Used for Randomization (per IWRS)	• Fludrocortisone replacement status (requires fludrocortisone or does not require fludrocortisone)
Baseline Assessments	

Participant's assessment of biochemical control

Sex

Assessments at V4, V5, V6 and V7	Participant's biochemical response status
Other	Randomized study treatment (Chronocort or IRHC)

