# 5.11.3.1.4 Combining Step

SAS Proc MIANALYZE will be used to combine the 50 point estimates for the common response probability difference and standard errors, allowing appropriate statistical inference as described below:

# 5.11.3.2 First Key Secondary Efficacy Endpoint – Dose Response at Visit 6

The approach for dose response will be similar to that described in Section 5.11.3.1 for biochemical response. The primary analysis conducted using MAR approach for imputation will be presented for this endpoint, similar to the primary efficacy endpoint.

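### Missing Visit 6 responses are imputed without the known dose and, as written, separately for two nested endpoints: a small effect that a short SAP change removes

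*SAP*

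**What the plan says.** SAP 5.11.2.1 counts discontinuation of treatment before Visit 6 as non-response and sends missing Visit 6 response data to multiple imputation. SAP 5.11.3.1 applies the intercurrent-event rule first, then imputes 50 times: "For the imputation of missing data, the binary response status will be multiple imputed". It adds: "As imputations will be for binary components, the models used for prediction and imputation will be logistic regression models".

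The predictor table in SAP 5.11.3.1.1 holds fludrocortisone status, baseline control, sex, arm and, as its only post-baseline entry, "Participant's biochemical response status" at V4 to V7. It lists neither dose nor androgen concentration.

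For the first key secondary endpoint, SAP 5.11.3.2 says: "The approach for dose response will be similar to that described in Section 5.11.3.1 for biochemical response". It gives no joint model, shared draws or consistency rule.

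In SAP 5.11.1.1 the dose limit for biochemical response is "not more than 25 mg (if the participant was in biochemical control at baseline"); otherwise it is 30 mg. For dose response (SAP 5.11.1.2) the limit is 25 mg for everyone. Dose decisions are entered in the IRT (Protocol 4.2). Protocol 4.1 says: "Once the titration visit at 16 weeks is complete and the dose adjusted, if necessary, the dose of study medication will then be fixed", to be kept to the end of the study where feasible. Protocol 4.4 states that the endpoints are nested: all "dose responders are biochemical responders: additionally, participants who were out of biochemical control at baseline" also count if they reach control on no more than the starting dose.

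**The concern.** Response needs both laboratory control and a dose within the limit. When only the Visit 6 blood result is missing, the dose is normally still known. The plan sets that knowledge aside and draws the combined status from a model that has not seen the dose. Two things can follow on a literal reading.

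- A participant who cannot be a responder is drawn as one.
- The two endpoints, apparently imputed in separate runs, disagree in a participant for whom they are the same event.

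The primary and first key secondary endpoints are tested in sequence on the same 50 or so people. SAP 9 records that the MNAR and tipping-point analyses were removed, so no planned MNAR check on this imputation remains.

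**Working it through.** **Step 1: what is unknown when only the Visit 6 sample is missing** (from SAP 5.11.1.1 and 5.11.1.2)

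| Baseline control | Recorded dose | Biochemical response | Dose response |
|---|---|---|---|
| Yes | 30 mg | No, certain | No, certain |
| Yes | 25 mg or less | Equals week 28 control | Equals week 28 control |
| No | 30 mg | Equals week 28 control | No, certain |
| No | 25 mg or less | Equals week 28 control | Equals week 28 control |

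In every row the only unknown is control. At 25 mg or less the two endpoints are one event.

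**Step 2: the plan's own figure** (SAP 3: 40% against 68%, margin 15 points, 25 per arm, one-sided 2.5%, continuity-corrected, unpooled)

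- Distance from the margin: 0.15 + 0.28 = 0.43.
- Variance: 0.40×0.60 + 0.68×0.32 = 0.4576. SE: √(0.4576/25) = 0.1353. Correction: 1/25 = 0.04.
- Power: Φ((0.43 − 0.04)/0.1353 − 1.96) = 82.2%.

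The claim of at least 80% reproduces, and the fix leaves it unchanged.

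**Step 3: weight of one impossible responder.** If drawn as a responder with probability p, the participant moves the arm's rate by p/25 on average: 0.4 points at p = 0.10, 1.6 at 0.40, 2.7 at 0.68.

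**Step 4: impossible pairs.** If the endpoints are drawn independently with probabilities p (biochemical) and q (dose), a dose responder who is not a biochemical responder arises with probability q(1 − p). For p = 0.68 and q from 0.1 to 0.6 this is 3% to 19%. For p = 0.40 and q from 0.1 to 0.4 it is 6% to 24%.

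**Step 5: how often this can happen under the listed predictors** (illustrative simulations; the rates are assumptions)

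- *Simulation A:* 25 per arm, 3 missing results, baseline control 20% to 60%, assumed titration rates, two separate logistic imputations using V4 and V5 status, 50 draws, 400 replicates. Certain biochemical non-responders were drawn as responders in 24–36% of draws, and certain dose non-responders in 18–26%. Of imputed pairs, 16–29% contradicted each other.
- *Simulation B:* 300 trials, 5 of 50 missing at random. The corresponding rates were 45% and 17%. At 25 mg or less the endpoints disagreed in 30% of draws, and 12% of pairs were impossible.

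**Step 6: effect on the result**

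- In Simulation B, imputing control and then applying the dose lowered the mean squared error of the imputed values from 0.193 to 0.172 (biochemical) and from 0.150 to 0.117 (dose). Mean bias among missing participants was −0.017 (composite) against −0.024 (component) for biochemical response, and 0.000 against −0.038 for dose response. Over the whole sample the largest is 0.038×5/50 = 0.4 points, and it belongs to the component method.
- A simplified simulation (600 trials per scenario, 3 or 5 missing) gave the same primary-endpoint SE to within 0.001 (0.137 with 5 missing). With 5 missing, non-inferiority was shown in 81.7% against 82.2% of trials in one scenario and 85.8% against 85.7% in another. Primary decisions differed in 1–3% of trials. Dose-response decisions differed in 4–6%, falling to 2–5% once known dose failures were set to non-response. Certain biochemical non-responders among the missing averaged 0.2–0.6 per trial.
- A further simulation (25 per arm, 5 missing) measured error in the treatment difference against complete data. Component imputation lowered the root mean squared error from 0.043 to 0.039 (biochemical) and from 0.040 to 0.034 (dose) under random missingness. It removed a bias of 1.0 to 1.8 points when missingness depended on dose within one arm.

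**The case against.** **Known dose failures may never reach the imputation.** SAP 5.11.2.1 and 5.11.2.2 deem anyone who does not meet the criteria a non-responder, and 30 mg with baseline control fails whatever the laboratory shows. This is a fair reading, and under it the impossible-responder rates above do not apply. But it stands as a restatement of the definition. SAP 5.11.3.1 pre-sets only data on or after an intercurrent event and says nothing of a known dose with a missing sample. The reading also leaves dose out of the model and the draws separate.

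**The code is not visible.** The example SAS code and the analysis appendix cannot be read, and the reference to binary components might mean component imputation. Separate runs are inferred from SAP 5.11.3.2. This stands as a limit: only the written specification was checked, and its predictor table names response status alone.

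**Contradictory draws break nothing formally.** A reader might infer that they invalidate the tests or the fixed sequence in SAP 5.11.8. They do not. Each endpoint has its own marginal estimate and Rubin combination, and the sequence needs two marginal decisions, not agreement within each participant.

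**Few people are affected.** Early leavers are already non-responders, stress dosing delays Visit 6 rather than losing it (Protocol 4.3), and week 34 can replace week 28 for earlier recruits (SAP 5.2.5). This stands. SAP 5.2.5 does allow for missing week 28 results, but no expected number is given.

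**The model already carries some dose information.** V4 and V5 response status includes the dose condition. This is partly right, but it misses a reduction made after V5.

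**The dose is not always certain.** It is fixed only where feasible, and Protocol 4.2 allows a reversion. A reader might infer that only the laboratory part can ever be missing; that goes too far.

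**Conclusion.** The concern holds as a gap in the written specification with a small expected effect. As written, SAP 5.11.3.1 and 5.11.3.2 leave out a component of the endpoint that is normally known, do not explicitly exclude impossible responders before imputation, and do not keep two nested endpoints consistent.

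SE and power barely change, and bias is negligible under random missingness. It reached about 1 to 2 points only in an illustrative simulation where missingness depended on dose within one arm. A reader might infer that the non-inferiority conclusion is unsafe or that the plan biases it in a known direction. The documents support neither: they give no missing rate and no sign that missing samples relate to dose.

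The sizes rest on assumed rates of baseline control, titration and missingness (3 or 5 of 50), and on reading the two imputations as separate. The change is a cheap improvement in method and is not needed to rescue the main result.

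**What to change.** In SAP 5.11.3.1, 5.11.3.1.1 and 5.11.3.2:

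1. State, as a step before imputation, that a participant whose recorded Visit 6 dose fails the endpoint's dose condition is a non-responder for that endpoint. If the Visit 6 dose is not recorded, use the last dose assigned in the IRT.
2. Impute one variable, biochemical control at 08:00 (yes/no), and add recorded dose to the prediction model as a single term, such as 30 mg against 25 mg or less, to limit sparsity.
3. In each of the 50 completed datasets, derive both endpoints from the same imputed control status and the recorded dose. Participants who discontinued treatment stay non-responders, as now.

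Impossible responders and contradictory pairs then fall to zero by construction.

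The cost is SAP rewording, a revised PROC MI call and one extra term in a small logistic model, for which SAP 5.11.3.1.2 already provides an augmented-likelihood option. No new data are needed, and sample size does not change.
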